8.6. Early Discontinuation or Withdrawal of Study Participants

Each participant has the right to withdraw from the study at any time for any reason without penalty. In those cases where a "withdrawal of consent" is requested by the participant, documentation of the withdrawal of consent and the reason(s) for the request will be captured in the participant's clinical research records and/or on the status change CRF. Although the participant is not obligated to give reason(s) for withdrawing, the investigator should make a reasonable effort to ascertain the reason(s) while fully respecting the participant's rights. The participant will also be asked if she/he will agree to complete the clinical assessments listed for the study termination/exit visit (Visit 6).

8.6.1. Investigator Withdrawal of Participants

The PI may withdraw a participant without their consent for the following reasons:

- Failure to comply with study procedures or requirements
- A participant's health or safety may be compromised by further participation
- The PI assesses that it's not in the best interest of the participant to continue participation in the study

If a participant is withdrawn by an investigator, the reason should clearly be stated in the source documents and on the status change CRF.

When a participant withdraws due to an AE or is withdrawn by the PI due to an AE, the sponsor's safety office, the USAMRDC ORA PSSO, must be notified within 5 business days ([contact]). Investigators must follow specific policies regarding the timely reporting of AEs and SAEs to the IRBs (Section 11.8.1.2).

8.6.2. Data Collected for Withdrawn Participants

Only data and samples already collected will be analyzed according to the protocol. The study team will not utilize samples or data from this participant for any future use if he/she has not consented to future use and will discard residual samples when the study is completed as is done for all participants who refuse storage and future use of their samples.

8.6.3. Replacement of Withdrawn Participants

Participants who withdraw or are withdrawn at any time prior to receiving the study injections until 30 days after receiving the injections may be replaced. A participant who has been assessed as eligible for the study through screening will take the place of the withdrawn participant.

Participants who withdraw or are withdrawn within this window will not count toward the total number of participants enrolled in the study.

8.6.4. Follow-up for Withdrawn Participants

After withdrawal, the study team will engage in no further communication with the participant except as directed by an IRB and/or USAMRDC regarding information concerning participant safety.

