9.3. Management of Participants Who Become Pregnant

Pregnant women and women who plan to become pregnant during the first 3 months after study vaccine administration are excluded from enrollment. If a participant becomes pregnant during the course of the study, they will continue to be followed for the remainder of the study period per the SOE, however the participant will be excluded from optional invasive procedures and blood draws will be conducted for safety purposes only. Every effort will be made to remain in contact with the pregnant participant until birth or termination of the pregnancy in order to record the outcome of the pregnancy.

Pregnancy outcomes will be recorded via a standardized pregnancy CRF. Information documented on this form will include date of last menstrual period, date pregnancy confirmed, history of complications during prior pregnancies (such as congenital abnormalities or spontaneous abortions) and pregnancy outcome information including date of termination or delivery, any complications of pregnancy, the gender, weight, and presence of any congenital abnormalities.

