9.4. Management of Participants Who Become Incarcerated

Participation of prisoners is not planned, and any participant will be suspended from study visits while incarcerated, except visits or telephone contact for the purpose of ensuring participant safety. No study product will be administered to a participant who is incarcerated. The IRBs (see [Table 5](#)) will be notified of the period of incarceration. Data and samples that were collected before the period of incarceration may still be stored and used for analyses. After release from incarceration, the participant may either return to participation in study visits according to the SOE or study participation may be terminated at the discretion of the PI.

Participants who have returned to the clinic after a period of incarceration will be counseled again about the potential risks of being a participant in the study. A note to the effect that the counseling was done will be written in the progress notes in the participant's binder.

Any participant who is incarcerated for more than 6 months will be re-consented to include taking and passing the TOU.

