11.8.2.3. Pregnancy

Each pregnancy must be reported to the USAMRDC ORA PSSO within 24 hours of identification by completing and submitting the Pregnancy Report Form by email or fax. Pregnancies must be reported within 48 hours of becoming aware of the event to the IRBs. WRAIR HSPB will forward the notification to USAMRDC OHARO OHRO as per USAMRDC Command Policy 21.

Participants who become pregnant after Day 0 will be followed to term, and the following information will be reported on the Pregnancy Report: type and date of delivery, Apgar scores, and health status of the mother and child including the child's gender, head circumference, gestational age at delivery, height and weight.

Complications and or abnormalities should be reported including any premature terminations. A pregnancy is reported as an AE or SAE only when there is suspicion that the investigational product may have interfered with the effectiveness of contraception or there was a serious complication in the pregnancy including a spontaneous abortion or an elective termination for medical rationale. Otherwise, pregnancy will not be categorized as an adverse event.

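### Protocol 8.6.4 ends study-team contact after every withdrawal unless an IRB or USAMRDC directs it, so injected participants who have not refused contact lose active safety follow-up before Day 336

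*Protocol*

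**What the plan says.** Protocol 8.6.4 has a single rule for everyone who leaves: the study team "will engage in no further communication with the participant except as directed by an IRB and/or USAMRDC regarding information concerning participant safety". It does not distinguish who initiated the withdrawal, whether the person was injected, or whether the person objects to contact. Section 8.6.2 adds: "Only data and samples already collected will be analyzed according to the protocol".

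Section 8.6.1 opens its list of grounds with "The PI may withdraw a participant without their consent for the following reasons". One ground is that continuing may compromise the participant's health or safety. The section then covers the case "When a participant withdraws due to an AE or is withdrawn by the PI due to an AE", for which the sponsor's safety office must be told within 5 business days.

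Elsewhere the protocol points the other way. Section 11.7.1 has AEs and SAEs collected from injection to the end of the study. On pregnancy, 9.3 says "Every effort will be made to remain in contact with the pregnant participant until birth or termination of the pregnancy" and 11.8.2.3 says "Participants who become pregnant after Day 0 will be followed to term". Section 7.3.3 keeps unblinded participants in follow-up for the whole trial. Section 9.4 suspends visits for incarcerated participants "except visits or telephone contact for the purpose of ensuring participant safety".

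**The concern.** Both injections are given on Day 0. Withdrawing someone afterwards cannot reduce exposure; it only ends the remaining procedures and the observation. Safety is the primary objective, and 7.1.1 includes AESIs because an adjuvant is used. A participant whom the PI withdraws for an AE or for health reasons is one whose later course is especially informative, and that person has not asked to be left alone. Under 8.6.4 active follow-up of that person stops by default, with no consent reason for stopping it.

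The analysis does not make up for this. The safety population (Protocol 12.2.1, SAP 5.3.1) keeps any injected participant with post-dose data, so someone withdrawn after Day 7 generally stays in the denominator while later events go unsought. Read literally, 8.6.2 would also leave out of the analysis an event learned of after withdrawal.

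**Working it through.** The plan states no figure on this point, so the check is mainly a reading of the sections together, followed by the follow-up time at stake.

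**Which rule applies to whom, after injection**

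- *Withdraws consent and refuses contact:* 8.6.4 is appropriate.
- *Withdraws consent but would accept a safety call:* 8.6 asks whether the person will complete the Visit 6 clinical assessments once. After that, 8.6.4 stops contact. No section provides for asking about calls.
- *Withdrawn by the PI without consent:* 8.6.1 specifies reporting only and does not repeat the exit-visit offer. 8.6.4 stops contact.
- *Withdrawn with a known pregnancy:* 9.3 and 11.8.2.3 require contact to outcome; 8.6.4 forbids it unless directed. No section says which prevails.

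**Follow-up lost per person**

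Inputs: post-dose visits on Days 1, 7, 14, 168 and 336 (Protocol 7.2); a 28-day AE reporting window (12.2.3); 7-day reactogenicity (11.2.2). The table assumes no exit assessment and no directed contact. Days lost = 336 − day last seen.

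| Last seen | Days lost | Share of 336 | Visits missed (of 5) | Days lost of the 28-day window |
|---|---|---|---|---|
| Day 7 | 336 − 7 = 329 | 97.9% | 3 | 28 − 7 = 21 |
| Day 14 | 336 − 14 = 322 | 95.8% | 2 | 28 − 14 = 14 |
| Day 168 | 336 − 168 = 168 | 50.0% | 1 | 0 |

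At the end of the replacement window in 8.6.3 (Day 30), 336 − 30 = 306 days (91.1%) would be lost. The 7-day reactogenicity data are complete in every row.

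**Effect on the zero-event bound (illustration)**

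The exact upper 95% limit with no events is 1 − 0.025^(1/n). For n = 16 it is 20.6%, which reproduces Protocol Table 7.

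- If one of 16 is not observed for late events, n = 15 gives 21.8%. The AE table shells define N as the Safety Population, so the figure computed on that N would still be 20.6%.
- If that person is replaced under 8.6.3, 17 are injected and 16 followed. The limit on N = 17 is 1 − 0.025^(1/17) = 19.5%, against 20.6% for the 16 observed.

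Either way the difference is about one percentage point per person (21.8 − 20.6 = 1.2; 20.6 − 19.5 = 1.1). It applies to late events only, and any loss to follow-up would have the same effect.

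**The case against.** The strongest reply is that the participant of most interest already has a route. USAMRDC's safety office learns of AE-related withdrawals within 5 business days (8.6.1, 11.8.2.5), it belongs to a body that 8.6.4 allows to direct contact, and Appendix A has it follow each reported event to resolution. Participants are told to contact the site about study-related illness (15.2.3). Section 11.7.2 says SAEs in former participants need not be actively sought but has related ones reported if they come to light, so passive surveillance is arguably a deliberate choice. The exit assessment sits under the parent heading 8.6 and may be read as covering every withdrawal. PI withdrawal is discretionary, and with a single dose there is little reason to use it. For pregnancy, the specific rule would normally prevail over the general one.

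Most of this stands as mitigation. Known and self-reported events are reasonably covered, and the affected group may be empty. But directed contact is optional, the exit assessment is a single voluntary visit, and none of these routes requires a search for a new event afterwards. Section 11.7.2 speaks of events that come to light after study completion; it does not justify ending contact before Day 336. The pregnancy conflict can be settled by interpretation, but a site should not have to do so.

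A reader might infer that one missed event would overturn the safety conclusion, for example 0/32 against 1/32 in the pooled ALFQ groups. That sensitivity belongs to any small sample and is not specific to 8.6.4. Nor is there a reporting gap: withdrawals, reasons and visit completion are reported by group (SAP 6.2, Table 5, Listing 2).

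**Conclusion.** The point holds as a limited design weakness. For injected participants whom the PI withdraws, or who stop visits but would agree to safety contact, 8.6.4 ends active finding of SAEs, AESIs and pregnancies before Day 336. This goes against 11.7.1 and contradicts 9.3 and 11.8.2.3 where a pregnancy is known.

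The loss is large for each person affected (50% to 98% of the 336 days, given no exit assessment and no directed contact) and probably small for the trial. The documents state no rate of PI or AE withdrawal, so the number affected is unknown and may be zero. No primary analysis, sample size or dosing decision is shown to change.

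Two stronger readings are not supported. Withdrawn participants do not drop out of safety oversight altogether, because the passive and discretionary routes remain. Nor should everyone who withdraws consent be telephoned by default; contact with them needs their recorded agreement. The consent forms were not available and may already address contact after withdrawal.

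**What to change.** Amend 8.6.4 so that:

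- (a) injected participants withdrawn by the PI are telephoned on the remaining scheduled days among 14, 168 and 336 about SAEs, AESIs and pregnancy, unless they decline;
- (b) participants who withdraw consent are asked at withdrawal whether they agree to such calls, the answer is recorded, and they are called only if they agree, with IRB- or USAMRDC-directed contact kept as now;
- (c) a known pregnancy is followed to outcome as in 11.8.2.3, unless the participant refuses.

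Amend 8.6.2 so that safety data collected under 8.6.4 are analyzed. Sections 7.3.3, 9.3 and 9.4 already provide models.

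The cost is wording in two sections, possibly a consent-form line, and at most three calls per affected person (three after Day 7, two after Day 14, one after Day 168). If four people were affected, an assumption, that is at most 4 × 3 = 12 calls. No extra participants, visits or samples are needed. The calls rely on self-report and do not replace the missed laboratory or pregnancy tests.

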9. STUDY PROCEDURES

9.1. Vaccination and Follow-up Visits

9.1.1. Day 0 Through Day 336

Day 0 is defined as the day of protocol enrollment and vaccine/placebo injections. At the enrollment visit, screening results will be reviewed and general eligibility will be assessed. All screening results, including results from any repeat testing, must be received prior to enrollment. Repeat testing will not affect the post-screening enrollment window (see [Table 3](#)) unless the repeat testing is necessary to establish a baseline CD4 count, in which case enrollment will occur no sooner than 16 days after the date that blood was drawn for the baseline CD4 count.

If clinical assessment on Day 0 suggests significant changes may have occurred since the screening visit, then the physical examination, complete blood count, prothrombin / international normalized ratio of partial thromboplastin time, blood chemistries and urinalysis done at screening must be repeated, as appropriate, and results received before the participant receives the study injections. Pregnancy test results for female participants must be obtained prior to the study injections.

After Day 0, deviations from the visit windows in completing study visits are discouraged and will be recorded as protocol deviations, but are permitted, at the discretion of the PI (or designee), in consultation with the sponsor, in the interest of obtaining participant safety and immunogenicity evaluations following study injections.

Study visit procedures and tests through Day 336 include the following as indicated in the SOE ([Table 3](#)):

- Clinical evaluations: targeted physical examination and vital signs (both pre- and at about 30 minutes post-vaccination on Day 0)
- Interim medical history, including any new medications taken
- Adverse event documentation
- Study vaccine/placebo injections
- Diary Card: Baseline in the evening on the day of the injections; 7-day diary card for self-assessment by participant
- HIV risk assessment and risk counseling
- HIV testing (including pre/post-test counseling)
- Urine pregnancy testing and counseling
- Urinalysis
- CBC w/ diff
- CD4
- Optional Procedures:
 - Leukapheresis (with safety tests before and after procedure) (Day 14)
 - Sigmoid Biopsy (with GI and dietary questionnaires and safety tests prior to biopsy) (Day 14)
 - Lymph node biopsy (with safety tests prior to biopsy) (Day 14)

- Mucosal secretion collection, plasma LH and FSH (cervical secretions only) and Female Genital Tract (FGT) Questionnaire (Days 0, 14, 168 and 336)
- Endocervical cytobrush/swab and FGT Questionnaire (Days 0, 14, 168 and 336)

At intervals specified in the SOE, blood will be drawn for safety and immunologic assays. For participants who weigh >50 kg, the total blood volume drawn from each participant will not exceed 450 mL in any 12-week period. For participants who weigh ≤ 50 kg, the total blood volume drawn from each participant will not exceed 350 mL in any 12-week period.

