Endocervical Cytobrush/swab ^{2,7}		X			X	X	X	
Pap Smear, if none available in last two years ⁷	X							
Sigmoid Biopsy ^{3,7}					X			

Visit	S1	1 ¹¹	2	3	4	5	6 (Exit)	7
Visit Day	-45 to -16	0	1	7	14	168	336	post database lock
Visit Week		0	1	1	2	24	48	
Visit Month		0			0.5	6	12	
Visit Window			+2d	-/+2d	-2/+3d	-/+7d	-/+7d	
Lymph Node Biopsy					X			
Leukapheresis ⁴					X (10ml)			
Safety Tests for Biopsy or Leukapheresis (up to max possible volume) ¹⁰					20			
Research								
HIV Binding Antibody		SP			SP	SP	SP	
HIV Neutralizing Antibody Assays		6			6	6	6	
Functional Antibody Assays		SP			SP	SP	SP	
B-Cell Analysis ⁶		30		30	30	30	30	
Multiparameter Flow Cytometry		20			20	20	20	
Innate Cell Analysis		20	20	20	20	20	20	
Transcriptomics		20	20	20	20	20	20	
Additional Immunogenicity Testing ⁶		30		30	30	30	30	
Daily Volume (mL)	15	128	42	105.5	157.5	137.5	137.5	
Daily volume (mL) for participant weighing below 50 kgs	15	93	42	70.5	122.5	137.5	137.5	
Cumulative Volume (mL)	15	143	185	290.5	448	585.5	723	
Cumulative Volume (mL) for participant weighing below 50 kgs	15	108	150	220.5	343	480.5	618	
12-Week Cumulative Volume (mL)⁶					448	137.5	137.5	
12-Week Cumulative Volume (mL) for participant weighing below 50 kgs⁶					343	137.5	137.5	

SP = Assay performed from stored plasma, no additional blood volume required

¹ Full physical examination at screening (Visit S1) and targeted physical examination at all other visits.

² FGT questionnaire (Appendix J) will be administered to all participants who choose to undergo mucosal secretion collections and/or endocervical cytobrush/swab for microbiome/proteome assessment and cell collection prior to procedure at each collection visit

³ Gastrointestinal and dietary questionnaires (Appendix I & Appendix K) will be administered to all participants who choose to undergo a sigmoid biopsy and/or rectal swab for microbiome/proteome assessment prior to the procedure at each collection visit

⁴ Participants undergoing leukapheresis at Visit 4 will not have peripheral blood drawn for B-cell analysis, multiparameter flow cytometry, innate cell analysis, transcriptomics, or additional immunogenicity testing. In addition to the blood drawn for the remaining tests on the SOE, 8.5ml of blood will be collected by phlebotomy for PBMC and plasma storage. Red blood cell loss from leukapheresis is estimated to be 10mL.

⁵ Participants will be contacted for the unblinding visit after the clinical data is locked.

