⁶ The blood volumes drawn are in accordance with the Thai National Blood Bank policy: donation every 3 months but no more than 4 times a year; the amount of blood for each donation is according to weight that applies to both male and female: >50 Kg, 450 mL; ≤50 Kg, 350 mL. For participants who weigh below 50 Kg, blood for “Additional Immunogenicity Testing” will not be collected at Visits 1, 3 and 4 and only 25 mL of blood will be collected for “B-Cell Analysis” at Visits 1, 3, and 4.

⁷ Participants who consent for optional mucosal collections (semen, penile, rectal, and cervico-vaginal secretions, and cytobrush) and sigmoid biopsies will undergo additional testing for gonorrhea/chlamydia genital infections. Female participants who consent for optional mucosal collections will also undergo a pelvic examination that includes a Pap smear (if not done in 2 years prior to the mucosal collection) and visual inspection to evaluate for abnormalities. Female participants who choose to self-insert the menstrual disc collection device will be given instructions for self-insertion ([Appendix T](#)). Male participants who consent for optional mucosal collections will undergo a brief visual examination at the screening visit to assess the presence of urethral inflammation and will be given instructions for self-collection ([Appendix U](#)). Abnormalities that affect the participant’s safety or welfare or those that would increase the risk to a participant will preclude their participation in optional procedures.

⁸ Vitals to be collected both pre- and at about 30 minutes post-vaccination at Day 0.

⁹ Due to the time required to receive results of HIV testing, post-test counseling will occur at the next study visit after the results are available. HIV testing will be completed as described in Section [11.1.4.4](#) and management of positive results will be as described in Section [9.5](#).

¹⁰ Up to 10mL of blood will be drawn for safety tests within 2 days before the biopsy procedures for safety purposes. For the leukapheresis procedure, up to 10mL of blood will be drawn for safety tests within 2 days before and after the procedure for a total of 20mL of blood collected across both blood draws.

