Daily Volume (mL)	15	128	42	105.5	157.5	137.5	137.5	
Daily volume (mL) for participant weighing below 50 kgs	15	93	42	70.5	122.5	137.5	137.5	
Cumulative Volume (mL)	15	143	185	290.5	448	585.5	723	
Cumulative Volume (mL) for participant weighing below 50 kgs	15	108	150	220.5	343	480.5	618	
12-Week Cumulative Volume (mL)⁶					448	137.5	137.5	
12-Week Cumulative Volume (mL) for participant weighing below 50 kgs⁶					343	137.5	137.5	

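### The 350 mL blood cap starts at ≤50 kg but the reduced draws start only below 50 kg, so a participant recorded at exactly 50 kg who does not have leukapheresis is scheduled for 428 mL by Visit 4

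*Protocol*

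**What the plan says.** The cap appears in two places in the protocol, with the same cut-off in both.

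- Section 9.1.1: "For participants who weigh ≤ 50 kg, the total blood volume drawn from each participant will not exceed 350 mL in any 12-week period". For those above 50 kg, "the total blood volume drawn from each participant will not exceed 450 mL in any 12-week period".
- Table 3, footnote 6, which refers to Thai National Blood Bank policy and allows blood "according to weight that applies to both male and female: >50 Kg, 450 mL; ≤50 Kg, 350 mL".

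The reduction that is meant to meet the lower cap uses a different cut-off.

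- The next sentence of footnote 6 opens with its own weight limit: "For participants who weigh below 50 Kg, blood for". It then drops the sample for Additional Immunogenicity Testing on the first, third and fourth visits, and on those visits cuts the B-Cell Analysis sample from 30 to 25 mL.
- The reduced-volume rows of Table 3 carry the same limit in their labels, for example "Cumulative Volume (mL) for participant weighing below 50 kgs".
- SAP Table 2 (Section 4.1) repeats these rows: "Daily volume (mL) for participant weighing below 50 kgs".

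Footnote 4 of Table 3 matters for the exception: "Participants undergoing leukapheresis at Visit 4 will not have peripheral blood drawn for B-cell analysis". The other large research draws at that visit are also omitted for these participants.

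**The concern.** At exactly 50 kg the two cut-offs part. The cap is 350 mL, but neither footnote 6 nor any row of Table 3 reduces the draws, so site staff reading the schedule would take the standard volumes. By Visit 4 they would either pass the limit that the same footnote states, or have to choose which tubes to leave out without an instruction in the protocol. The limit concerns how much blood a healthy volunteer gives, and the sponsor adopted it from national policy. The operating rule should deliver it at every weight it covers.

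**Working it through.** **Inputs.** Volumes in mL from Table 3. Reductions from footnote 6, leukapheresis rules from footnote 4, optional safety draws from footnote 10. Caps from Section 9.1.1.

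**Step 1. Reproduce the standard total.**

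- Screening: 2 + 3.5 + 3.5 + 6 = 15
- Visit 1: 2 + 6 + 30 + 20 + 20 + 20 + 30 = 128
- Visit 2: 2 + 20 + 20 = 42
- Visit 3: 2 + 3.5 + 30 + 20 + 20 + 30 = 105.5
- Visit 4, required draws: 2 + 3.5 + 6 + 6 + 30 + 20 + 20 + 20 + 30 = 137.5
- Visit 4 with the 20 mL allowance for optional-procedure safety tests: 157.5

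Sum: 15 + 128 + 42 + 105.5 + 157.5 = 448, as printed.

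**Step 2. Reproduce the reduced total.** At each of Visits 1, 3 and 4 the reduction is 30 mL (Additional Immunogenicity Testing) plus 5 mL (B-Cell Analysis, 25 in place of 30), so 3 × 35 = 105. Then 448 − 105 = 343, as printed. The table's addition is correct.

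**Step 3. Check that one 12-week window holds all the draws.** Screening is at the earliest on Day −45 and Visit 4 at the latest on Day 14 + 3. The span is at most 45 + 14 + 3 = 62 days, inside 84 days.

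**Step 4. Exactly 50 kg, no leukapheresis, as written.**

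- Given by Visit 3: 15 + 128 + 42 + 105.5 = 290.5
- Left under the cap: 350 − 290.5 = 59.5
- Required at Visit 4: 137.5
- Total: 290.5 + 137.5 = 428, which is 428 − 350 = 78 over
- With one biopsy safety draw of up to 10 mL: up to 438, which is 88 over

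The 428 mL is not printed. It is the printed 448 mL less the 20 mL optional allowance.

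**Step 5. Exactly 50 kg, with leukapheresis.** Visit 4 becomes 2 + 3.5 + 6 + 6 + 8.5 + 20 + 10 = 56, where 8.5 is the storage sample, 20 the safety tests and 10 the red-cell loss. The total is 290.5 + 56 = 346.5, within the cap. This follows Table 3 in not counting the roughly 150 mL of plasma removed (Section 9.1.5). It keeps the 6 mL neutralizing-antibody sample, which Section 9.1.5 could be read as dropping. The total would then be 340.5.

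**Step 6. Exactly 50 kg, no leukapheresis, with the reduction applied at ≤50 kg.** 428 − 105 = 323. With one biopsy draw it is 333, and with the table's full 20 mL allowance 343. All are below 350.

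**The case against.** The strongest reply is that Section 9.1.1 states the cap without exception and footnote 6 states it again, both at ≤50 kg. Read as a whole, the protocol forbids the excess, and what remains is loose wording at a single weight. Most of this stands. The governing threshold is right, and a reader who infers that the protocol permits 428 mL at 50 kg goes further than the text. But a cap that the visit schedule contradicts leaves the site to find the conflict itself, probably at Visit 4 when only 59.5 mL is left. The Clinical MOP may settle it, but it is not among the documents.

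It is also fair that the affected group is very small, that leukapheresis participants stay within the cap, and that SAP Table 2 is given only for reference and adds no separate fault.

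A reader might also infer that re-screening breaks the 450 mL cap above 50 kg, because Table 3 counts one screening visit: 428 + 15 = 443, and a 10 mL biopsy draw gives 453. The documents do not support this as a fault. The cap covers any 12-week period, so repeat-screening blood already counts toward it. Footnote 10 makes 10 mL a maximum, so a draw of 7 mL or less keeps the total at or below 450.

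**Conclusion.** The point holds as a minor inconsistency. The cap and the reduction use different cut-offs, and following the reduction rule as written takes a 50 kg participant without leukapheresis 78 mL over the cap (22% of 350), or up to 88 mL with one biopsy safety draw. A reader might take this as an error in the table's totals, but those add up exactly. No endpoint or analysis is affected.

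The figures rest on the volumes stated in Table 3. Hormone samples (LH and FSH) are listed there without a volume, and Section 9.1.1 allows some blood tests to be repeated on Day 0. Neither is counted, so totals for participants who have them would be somewhat higher.

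How many participants are affected depends on how weight is recorded, which the documents do not say. As an assumption, rounding to whole kilograms would make a recorded 50 kg cover about 49.5 to 50.4 kg. Rounding to one decimal would make it 49.95 to 50.04 kg.

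**What to change.** Replace *below 50* with *≤50* in the second sentence of footnote 6 and in the reduced-volume row labels of protocol Table 3 and SAP Table 2. No printed volume changes, and no further rule is needed.

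The cost is 105 mL less research blood over Visits 1, 3 and 4 from a 50 kg participant without leukapheresis, the same reduction already accepted below 50 kg. One who has leukapheresis already skips those draws at Visit 4 and would give 2 × 35 = 70 mL less, at Visits 1 and 3.
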